Study Title

Does Transesophageal Echocardiography Along With an Orogastric Tube Improve the Image Quality Intraoperatively?

NCT03454399

01/10/2017

Study protocol

Objectives:

Assess the echocardiography image quality before and after suctioning orogastric tube attached to transesophageal echocardiography (TEE) probe.

Study Design:

Clinical trial with two-point evaluation at a single tertiary care medical center.

Methods:

Study population include surgeries which meet intraoperative TEE indication.

Preoperatively, the investigators attach a 16 French OG tube (COVIDIEN llc, Mansfield, MA. USA) to X7 TEE probe (Philips Medical Systems, Andover, MA) using a silk surgical suture (OGT-TEE probe). All patients give their written consent to participate in this study preoperatively. All patients receive general anesthesia with endotracheal intubation, standard American Society of Anesthesiologists monitoring, arterial blood pressure monitoring, central venous pressure monitoring, pulmonary artery pressure monitoring, and TEE. The demographics and characteristics of these patients are collected from our computerized patient database.

Data Acquisition

TEE images are collected using an iE33 echocardiographic machine (Philips Medical Systems, Andover, MA, USA) with an OGT-TEE probe. After induction of general anesthesia, regular OG tube is placed and removed after suctioning stomach. Then OGT-TEE probe is inserted.

Transgastric left ventricle short axis view (TG LV SAX) and midesophageal 4 chamber views (ME 4CV) are captured for 5 consecutive beats before and after suctioning OGT-TEE probe. Images with significant wall motion abnormality are excluded from assessment. For open heart surgeries, this is when coming off cardiopulmonary bypass (CPB); while for OLT cases, this is done when reperfusion or surgeons complained about distended stomach. Suction is performed for 1 minute at > -110 cm H₂O, and amount and characteristics of suction content is recorded. While acquiring these views, TEE device setting is not changed and iSCAN button is used before movie acquisition.

Measurements

Three investigators A, B and C, working independently, evaluate LV FAC and RV FAC for all images. Thus, 47×3 sets of images for each are investigated to obtain inter-observer variability. Subsequently, following an interval of between 6 and 8 months, investigator C again analyze all images to obtain intra-observer variability. In addition, these 3 investigators are asked to categorize image quality as numbers based on each investigator's impression (1: very bad, 2: bad, 3: acceptable, 4: good, and 5: very good) before and after suctioning.

Statistical Analysis

Continuous variables with normal distribution are displayed as the mean \pm standard deviation, while those variables with non-normal distribution as median and interquartile range. Categorical variables are presented as proportions and absolute numbers. For continuous variables, the normality test is performed using the Kolmogorov-Smirnov test. The differences between the 2 groups are investigated using the chi-square test or Fisher's exact test if any of the expected frequency <5 for categorical variables, and unpaired and paired Student t-test or the Mann-Whitney U test for continuous variables. The differences between the 3 groups are investigated using Fisher's exact test for categorical variables, and one-way ANOVA test or Kluskal-Wallis test for continuous variables. Intraclass correlation coefficient (ICC) is a widely used reliability index in intrarater and interrater reliability analyses. Intraobserver and interobserver reliability analyses of LV FAC and RV FAC are performed using ICC. We obtain consistency ICC for interobserver variability using all three investigators, and absolute-agreement ICC for intraobserver variability using investigator C, who measure all images twice with an interval between 6 and 8 months. All the statistical analyses are performed with R (version 3.4.3). A p-value of less than 0.05 is considered statistically significant

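### Normality is judged by a Kolmogorov-Smirnov test with no correction for estimated mean and SD, so moderate skew would usually be missed and described by mean and SD; naming a suitable test is a free improvement

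*Combined protocol and SAP*

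**What the plan says.** All of this is in the Statistical Analysis section of the combined protocol and SAP, except where stated.

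- The normality check: "For continuous variables, the normality test is performed using the Kolmogorov-Smirnov test". No mean or SD is specified in advance for any variable, no correction for estimating them is named, and no R function is given (only R 3.4.3).
- What the check decides explicitly: "Continuous variables with normal distribution are displayed as the mean" with SD, "while those variables with non-normal distribution as median and interquartile range".
- What it seems to decide: two-group comparisons use "unpaired and paired Student t-test or the Mann-Whitney U test for continuous variables", and three-group comparisons use "one-way ANOVA test or Kluskal-Wallis test for continuous variables". The section does not write down what selects within each pair.
- Level: "A p-value of less than 0.05 is considered statistically significant". The normality test has no separate level, so 5% is assumed to apply to it.
- Size: the Measurements section says "47×3 sets of images for each are investigated to obtain inter-observer variability". I take 47 as the number of values for one variable. Group sizes are not given.
- A variable that may be skewed, from Data Acquisition: "amount and characteristics of suction content is recorded". Its distribution is not given.

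**The concern.** The ordinary Kolmogorov-Smirnov test compares the sample with a normal distribution whose mean and SD are known beforehand. The plan supplies neither, so in practice they come from the sample under test. The fitted curve then follows the data too closely, the test statistic is too small for the standard critical value, and the test falls far below its nominal level. Its power against skew falls with it.

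At stake is whether the plan's own reporting rule works. A variable that should be given as median and interquartile range would often be given as mean and SD. If the same result also selects the comparison test, such a variable would go to the t-test or ANOVA rather than to the rank alternative. For before-and-after comparisons there is a further gap: the paired t-test rests on the distribution of the within-patient differences, and the plan does not say that these are what is checked.

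**Working it through.** The documents state no error rate or power for this step, so there is no figure of theirs to reproduce. The check is by simulation.

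**Inputs.** n=47 (Measurements); nominal level 5% (Statistical Analysis). Assumed: the skewed shapes, every other n, and the 24 v 23 split.

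**Step 1: statistic and thresholds.** For each sample, z = (x − sample mean) / sample SD, and D is the largest distance between the empirical distribution of z and the standard normal distribution. At n=47 the 5% critical value of D is 0.194 when the parameters are known. When they are estimated (Lilliefors) it is 0.128. The uncorrected threshold is therefore 0.194 / 0.128 ≈ 1.5 times too high.

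**Step 2: rejection rates at n=47** (20,000 samples per shape; 3,000 to 4,000 for Shapiro-Wilk).

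| Assumed shape | KS, uncorrected | Lilliefors | Shapiro-Wilk |
|---|---|---|---|
| Normal | 0.01% to 0.02% | 5% | 5% |
| Gamma, shape 4 (skewness 1) | 1.5% | 39% | 67% |
| Gamma, shape 2 (skewness 1.4) | 7% | 68% | 93% |
| Lognormal, log SD 0.5 | 10% | 68% | 90% |
| Exponential (skewness 2) | 33% | 95% | 99.9% |
| Lognormal, log SD 1 | 77% | 99% | 100% |

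Repeat runs agree to within about one to two points; for gamma with shape 2, Lilliefors came out between 66% and 68%.

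**Step 3: dependence on n.** The uncorrected test rejects an exponential variable in 7% of samples at n=24, 33% at n=47, 90% at n=94 and 99.8% at n=141. The weakness is greatest in subgroups and fades in larger sets.

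**Step 4: power of the procedure as it would be run.** Assume 24 v 23 lognormal values with a shift of 0.8 log SD. Use Mann-Whitney if the uncorrected test rejects in either group, and the t-test otherwise.

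| Log SD | Two-stage | Always Mann-Whitney | Loss |
|---|---|---|---|
| 0.5 | 73% | 74% | about 1 point |
| 0.75 | 71% | 74% | about 3 points |
| 1.0 | 72% to 73% | 74% | 1 to 2 points |

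Testing the 47 values pooled gives nearly the same: 72% to 73%, 71% and 72% to 73%.

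**Step 5: type I error of the t-test at n=47** (shapes: gamma with shape 4, exponential, lognormal with log SD 0.5 and 1).

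- Two-sample: 4.0% to 4.9%.
- Paired, where both measurements are equally skewed: 4.1% to 5.0%.
- Paired, where the differences themselves are skewed: 5.4% (gamma, shape 4), 6.8% (exponential), 10.4% (lognormal, log SD 1).

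**The case against.** **The plan does not say that the test is uncorrected.** The sponsor may have meant the Lilliefors version. This stands in part: the missing correction is inferred from the test's name. But the plan offers no source for the parameters other than the sample, and Lilliefors is a different test that would have to be named. The edit is the same on either reading.

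**A reader might infer that the test almost never rejects.** That is true for normal data, where not rejecting is correct, and close to true for mild skew. It fails for strong skew (77% for lognormal with log SD 1) and for larger samples. The supportable claim is that moderate skew is usually missed at n=47.

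**A reader might infer a large loss of power by comparing a t-test used throughout with Mann-Whitney used throughout.** The plan prescribes neither. Even the weak pre-test diverts many of the most skewed samples to Mann-Whitney, which brings the loss down to the 1 to 3 points shown.

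**A reader might say that the plan breaks its own rule for choosing the comparison test.** Only the choice between mean with SD and median with interquartile range is written. That normality selects between the t-test and Mann-Whitney is the natural reading, but it is not stated.

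**The objective is barely touched.** This largely stands. Image quality is scored 1 to 5, and ties in such a score push even the uncorrected test towards rejection; how that score should be analysed is a separate matter. Reliability of LV and RV FAC is assessed by ICC with no normality pre-test stated. No between-group comparison of suction amount is specified.

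**Conclusion.** The point holds in limited form. With sample estimates and no correction, the named test has a level near 0% and would often let skewed variables through as normal, contrary to the written rule on summaries. The damage is mainly to description. The loss of power is a few points at most in the scenarios tried. False positives are little affected, except where paired differences are themselves strongly skewed.

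The conclusion rests on three assumptions: the test is run as named, with estimated parameters; the 5% level applies to it; and some continuous variables have shapes like those simulated. The documents give no distributions. None of this supports a claim that the study's main comparison is invalid. The label is free improvement: a better method is available at essentially no cost.

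**What to change.** In the Statistical Analysis section:

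1. Replace the Kolmogorov-Smirnov test with Shapiro-Wilk read alongside a Q-Q plot, or name the Lilliefors-corrected version explicitly. Either restores the 5% level. Shapiro-Wilk had the higher power for every skewed shape in the table above.
2. For paired comparisons, apply the check to the within-patient differences.
3. State that the result selects between the parametric and the rank test. The only two-group rank test now named is an unpaired one, so the rank alternative for paired data should be named in the same sentence.

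The cost is one changed test name and one or two added sentences. No new data are needed and the software stays the same.

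### The plan assigns no test or unit to the within-patient before/after quality score, and its only paired difference test is the t-test, with no paired fallback

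*Combined protocol and SAP*

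**What the plan says.** The Objectives section states the aim: "Assess the echocardiography image quality before and after suctioning orogastric tube". Data Acquisition has each patient imaged at both time points in two views, the transgastric short-axis view and the four-chamber view: "midesophageal 4 chamber views (ME 4CV) are captured for 5 consecutive beats before and after suctioning OGT-TEE probe". The comparison is therefore within patient.

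Under Measurements, the raters of the fractional area changes (FAC) also score quality: "these 3 investigators are asked to categorize image quality as numbers based on each" investigator's impression, on a five-point scale, before and after suction. The only count given is for FAC reliability: "47×3 sets of images for each are investigated to obtain inter-observer variability".

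Statistical Analysis chooses tests by variable type and number of groups. It first says: "For continuous variables, the normality test is performed using the Kolmogorov-Smirnov test". Then: "The differences between the 2 groups are investigated using the chi-square test", with Fisher's exact test for small expected counts, and "unpaired and paired Student t-test or the Mann-Whitney U test for continuous variables". The quality score is not mentioned in that section. Nothing says whether it is continuous or categorical, which test compares before with after, or how three raters and two views become one analysis value. The reliability analysis (ICC) covers FAC only.

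**The concern.** Mann-Whitney, chi-square and Fisher's exact tests all assume independent groups. They have a proper place here, because the trial includes different patient groups: "For open heart surgeries, this is when coming off cardiopulmonary bypass (CPB); while for OLT cases". Naming them is not the fault. The fault is that the before/after comparison has no paired alternative once the t-test is set aside, and a five-point score is just the kind of variable for which an analyst may set it aside.

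Two choices are left open, and they can push the result in different directions:

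- **Test.** An unpaired test on one value per patient per time point ignores the positive correlation between a patient's two scores, so a real improvement can be missed.
- **Unit.** Treating three ratings of the same image as three independent observations can make the evidence look stronger than it is.

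**Working it through.** The plan gives no effect size, SD, correlation or power, so there is no stated figure to reproduce. The text alone establishes the gap; the numbers below only show its possible size.

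**Inputs.** From the documents: a five-point score, three raters, two time points, significance at 0.05 (taken as two-sided), and 47, inferred as the number of patients from the count given for FAC. Assumed: a latent normal score with a shift of 0.4 SD after suction, before/after correlation ρ from 0 to 0.7, and five sets of cut-points that turn the latent score into 1 to 5.

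**Step 1: closed form on the latent scale, ρ = 0.5.**
- Paired: z = 0.4 × √47 / √(2(1 − ρ)) = 0.4 × 6.856 / 1 = 2.742. Power = Φ(2.742 − 1.96) = Φ(0.782) = 78%.
- Unpaired: the statistic is centred at 0.4 × 6.856 / √2 = 1.939, but its true SD is √(1 − 0.5) = 0.707. Power = Φ((1.939 − 1.96) / 0.707) = Φ(−0.030) = 49%.
- Unpaired type I error: 2[1 − Φ(1.96 / 0.707)] = 2[1 − Φ(2.772)] = 0.6%, against a nominal 5%.

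At ρ = 0 the two calculations coincide.

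**Step 2: simulation on the five-point score** (one score per patient per time point, 20,000 replicates per cell, ranges over the cut-point sets). Power in %, except the last row:

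| Latent correlation | 0 | 0.3 | 0.5 | 0.7 |
|---|---|---|---|---|
| Mann-Whitney | 43–44 | 42–44 | 41–43 | 39–41 |
| Signed-rank | 42–43 | 53–56 | 66–68 | 83–86 |
| Paired t | 43–44 | 55–57 | 67–69 | 84–86 |
| Screen, then paired t or Mann-Whitney | 43–44 | 42–54 | 41–63 | 39–76 |
| Mann-Whitney type I error, % | 4.4–5.2 | 2.0–2.3 | 0.8–1.0 | 0.1–0.2 |

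The fourth row covers several versions of the Kolmogorov-Smirnov screen. Whether a single score fails depends on the version: screening the before score rejects in 23–89% of trials with ordinary critical values and in 100% with Lilliefors values. With 30 pairs and ρ = 0.5 (two cut-point sets) the pattern is the same: Mann-Whitney 24–25%, signed-rank 45–48%, paired t 47–50%.

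**Step 3: score dichotomised at 4 or more, ρ = 0.5.** Chi-square/Fisher 20–22% (28–30% without continuity correction), exact McNemar 35–37%. At ρ = 0.3 the uncorrected chi-square loses nothing.

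**Step 4: mean of three raters.** Over five assumed variance splits, power is 58–68% for Mann-Whitney and 65–98% for paired t. If the mean is screened first with ordinary critical values, the screen-then-test rule loses at most about 0.7 points against paired t when the before mean is screened, and about 2 points when the difference is screened. With Lilliefors values the loss is roughly 1–27 points.

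**Step 5: raters stacked as 47 × 3 = 141 rows.** Let I be the variance that raters share within a patient and time point, and R the residual. Patient and rater effects cancel in the difference, so the paired t-test understates the variance of the mean difference by the factor (3I + R)/(I + R).
- I = R = 0.3: factor 1.2/0.6 = 2.0; type I error about 2[1 − Φ(1.96/√2)] = 17%.
- I = 0: factor 1; type I error 5%.

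Simulation agrees: 9.2–18.4% for paired t or signed-rank with I from 0.1 to 0.5 of total variance, and 4.0–5.8% for paired t with I = 0. For stacked Mann-Whitney the factor is (3I + R)/total, which can lie below or above 1; the simulated type I error is 1.5–14.6%.

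**The case against.** The strongest reply is that the plan already names an adequate test. A paired t-test on one value per patient performs as well as signed-rank throughout the table, and before/after suction is the obvious paired contrast in a two-point design. That stands, and it limits the harm. But the plan does not assign that test to the score or reduce three raters to one value, so the analyst is not bound to this route.

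Second, the link from a failed screen to Mann-Whitney is not written down. The plan ties normality to how variables are displayed and then lists tests. This also stands: the rule simulated here is the natural reading, not stated text. A reader might go further and infer that the plan prescribes an unpaired analysis of paired data, or that the score must fail the screen. The documents support neither. The outcome of the screen depends on the score distribution, the version of the test and what is screened.

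Third, a reader might infer that stacking raters always inflates the error. Step 5 shows that paired tests need shared image-level variance for this. Such variance is plausible, since all three read the same images, but the documents give no estimate.

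Finally, no primary endpoint is named, and the score is introduced after the FAC readings. Calling this the main comparison is an inference from the title and objective.

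**Conclusion.** The concern holds as a gap in prespecification with a possible material cost, not as a demonstrated error in the analysis. The before/after quality comparison has no assigned test or unit, and there is no paired option for non-normal or categorical data.

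If the open choice ends in Mann-Whitney on one score per patient, power falls by about 25 points at ρ = 0.5 (about 67% to about 42%) under the assumed 47 pairs and 0.4 SD shift. The loss vanishes at zero correlation, does not arise with the paired t-test on one value per patient, and is small if the three-rater mean is screened with ordinary critical values. Stacking raters can instead raise the type I error of paired tests to roughly 9–18% if raters share image-level variance. The size rests on assumptions; the gap rests on the text. It should be fixed before analysis.

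**What to change.** In Statistical Analysis, state that:

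- for each view, the three raters' quality scores are averaged to one value per patient per time point, and before is compared with after by the Wilcoxon signed-rank test, without a normality screen;
- any before/after comparison of FAC uses the same paired approach;
- McNemar's test is used if the score is dichotomised;
- raters are not treated as independent rows;
- the unpaired t-test, Mann-Whitney, chi-square and Fisher's exact tests are reserved for comparisons between different patients, such as open heart versus OLT.

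This gives one quality comparison per view, so the text should also say how the two are to be read together.

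The cost is wording only, with the same data and software. Against the paired t-test, signed-rank gives up at most a point or two of power when the differences are normal.

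### Inter-observer FAC reliability uses a consistency ICC and intra-observer an absolute-agreement ICC, so constant offsets between the three readers drop out and the two figures are not comparable

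*Combined protocol and SAP*

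**What the plan says.** Under Measurements, "Three investigators A, B and C, working independently, evaluate LV FAC and RV FAC for all images", and the plan adds: "Thus, 47×3 sets of images for each are investigated to obtain inter-observer variability". For the repeat reading, "following an interval of between 6 and 8 months, investigator C again analyze all images to obtain intra-observer variability".

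Under Statistical Analysis, "Intraobserver and interobserver reliability analyses of LV FAC and RV FAC are performed using ICC". The type of coefficient is then fixed: "We obtain consistency ICC for interobserver variability using all three investigators, and absolute-agreement ICC for intraobserver variability using investigator C".

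The plan does not explain why the two analyses use different types. It does not state whether the coefficients are single-measure or average-measure, whether readers are treated as random or fixed, or whether confidence intervals will be given. It plans no Bland-Altman limits and no table of mean differences between readers. The same section mentions a comparison of three groups by "one-way ANOVA test or Kluskal-Wallis test for continuous variables", without saying what the three groups are.

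**The concern.** Disagreement between readers has two parts. One is systematic: one investigator reads FAC higher than another by a roughly constant amount. The other is random or specific to the image. A consistency ICC removes the systematic part from its denominator and keeps the second part. An absolute-agreement ICC counts both.

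The plan therefore counts a systematic shift when it occurs within investigator C but not when it occurs between A, B and C. Two things follow. The inter-observer coefficient cannot reveal a reader who is constantly high or low, although the three sets of readings are collected to measure inter-observer variability. And the two coefficients answer different questions, so printing them together invites a comparison they cannot support: readers could appear to agree with each other better than C agrees with C when the opposite is true.

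What is at stake is the reported reliability of LV FAC and RV FAC.

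**Working it through.** The documents state no ICC, target ICC, FAC standard deviation or reader offset, so there is no planned figure to reproduce. The first step below follows from definitions; the rest uses assumed inputs.

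**Inputs from the plan.** Three readers (k = 3) for the inter-observer ICC; two readings by C (k = 2) for the intra-observer ICC; 47 image sets, taken as n = 47.

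**Assumed inputs, in FAC points.** Between-patient SD 10 or 15 (Vp = 100 or 225); residual SD 4 (Ve = 16); reader offsets -d/0/+d with d = 0, 2, 3 or 5. The sample variance of the three offsets is Vr = d², i.e. 0, 4, 9 or 25.

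**Step 1: definitions (single measure).**
- Consistency: Vp / (Vp + Ve)
- Absolute agreement: Vp / (Vp + Vr + Ve)

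Vr is absent from the first. As a check on one simulated 47 × 3 data set (between-image SD 10, error SD 5), adding offsets of 0, ±5 and ±10 left consistency at 0.854 each time, while absolute agreement went from 0.853 to 0.763 to 0.567.

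**Step 2: inter-observer ICC, single measure.**

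| Offsets | SD 10: consistency | SD 10: absolute | SD 15: consistency | SD 15: absolute |
|---|---|---|---|---|
| none | 100/116 = 0.86 | 100/116 = 0.86 | 225/241 = 0.93 | 225/241 = 0.93 |
| -2/0/+2 | 0.86 | 100/120 = 0.83 | 0.93 | 225/245 = 0.92 |
| -3/0/+3 | 0.86 | 100/125 = 0.80 | 0.93 | 225/250 = 0.90 |
| -5/0/+5 | 0.86 | 100/141 = 0.71 | 0.93 | 225/266 = 0.85 |

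Simulation (n = 47, 4000 runs, SD 10, offsets ±5) gave means of 0.857 and 0.702.

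**Step 3: average of three readers.** The forms are Vp/(Vp + Ve/3) and Vp/(Vp + (Vr + Ve)/3). With offsets -5/0/+5 they give 0.95 versus 0.88 (SD 10) and 0.98 versus 0.94 (SD 15). The unstated form therefore moves the planned consistency ICC between 0.86 and 0.95 at SD 10.

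**Step 4: comparability with the intra-observer ICC.** Suppose C shifts by 3 points between readings. For k = 2 the sample variance of (0, 3) is 4.5, so the intra-observer absolute-agreement ICC is 100/120.5 = 0.83 (SD 10) or 225/245.5 = 0.92 (SD 15). With readers at -5/0/+5:

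| | Inter-observer | Intra-observer |
|---|---|---|
| As planned, SD 10 | 0.86 | 0.83 |
| Both absolute agreement, SD 10 | 0.71 | 0.83 |
| As planned, SD 15 | 0.93 | 0.92 |
| Both absolute agreement, SD 15 | 0.85 | 0.92 |

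The order reverses in both cases. At SD 10 with offsets -3/0/+3 it also reverses, but narrowly (0.80 against 0.83). With -2/0/+2 it does not (0.833 against 0.830).

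**Step 5: precision.** McGraw-Wong 95% intervals with n = 47, k = 3, SD 10 and expected mean squares MSR = 3×100 + 16 = 316, MSE = 16, MSC = 47×Vr + 16:
- Consistency: 0.79 to 0.92, whatever the offsets
- Absolute agreement, offsets -2/0/+2 (MSC = 204): 0.72 to 0.90
- Absolute agreement, offsets -5/0/+5 (MSC = 1191): 0.27 to 0.87

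**The case against.** The case for leaving the plan alone has real content.

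- **Consistency is a legitimate, openly labelled choice.** This stands. If only ranking or within-reader change matters, it is defensible. But the plan offers no such reason and uses the other definition for investigator C.
- **The trial's objective is untouched.** This stands too. The aim is to "Assess the echocardiography image quality before and after suctioning orogastric tube attached to transesophageal echocardiography (TEE) probe". A constant reader offset cancels in each reader's before/after difference, and the ICCs do not cover the 1-5 quality score. The point concerns a supporting result.
- **The plan proposes no comparison of the two ICCs, and the reversal rests on chosen inputs.** Correct. Offsets of -5/0/+5 mean 10 points between the extreme readers. In that SD 10 example the planned values of 0.86 and 0.83 have overlapping intervals (about 0.79 to 0.92 and 0.64 to 0.91), and small offsets change little. Nevertheless, the omission of offsets from the inter-observer figure holds without any comparison.
- **The absolute-agreement interval is wide with three readers.** True, and widest where offsets are large. That is a reason to show mean differences beside it; the narrower consistency interval is narrower because it does not address the offsets.
- **The three-group test may already compare readers.** The investigators are the only explicit threefold division in the documents, so this is possible. But the groups are not defined, a one-way test would ignore that the same images are read by all three, and it would leave the ICC as it is.

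The missing single- or average-measure statement is a separate and smaller omission that would not carry the point alone.

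**Conclusion.** The concern holds. That the planned inter-observer ICC excludes constant reader offsets, while the intra-observer ICC includes a constant shift, follows from the definitions and needs no trial data. The size cannot be derived from the documents. Under the assumed SDs, the inter-observer figure is overstated relative to absolute agreement by anything from nothing (no offsets) to 0.86 - 0.71 = 0.15 (SD 10, offsets -5/0/+5), or 0.93 - 0.85 = 0.08 at SD 15. It is an unexplained mismatch in a supporting reliability analysis, not an invalid statistic. It should be corrected because correction is cheap.

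**What to change.** In the Statistical Analysis section:

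1. Specify a two-way absolute-agreement ICC with 95% CI for both inter-observer and intra-observer reliability of LV FAC and RV FAC, in the same stated form (single-measure).
2. Report the pairwise mean differences between investigators A, B and C, and the mean difference between C's two readings.
3. Keep the consistency ICC, if wanted, as a supplement labelled as such.

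The cost is a changed ICC type, a stated form, confidence intervals and one short table; no further images, readings or patients are needed. The downside is that the reported inter-observer ICC may be lower and, where readers differ systematically, its interval will be wide because only three readers inform the reader variance. The mean differences show directly whether an offset exists and how large it is.
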